Subjects in this study will be males or females 18 years of age or older. Subjects must have histologically confirmed stage III NSCLC deemed surgically resectable by a thoracic surgeon with lobectomy, have adequate organ and marrow function, no prior history of active autoimmune disease or active infections, and have an ECOG performance status of 0-1. Patients with a prior history of chest radiation, interstitial lung disease/pneumonitis, or who would require a pneumonectomy, will be excluded.

Study Assessments and Criteria for evaluation:

Safety Assessments:

1. Safety:

All adverse events (including serious and non-serious, as well as adverse events of special importance AESIs) will be recorded from commencement of therapy until 30 days after surgical resection or 100 days after the last dose of immunotherapy, whichever is longer. Adverse events will be collected and recorded according to CTCAE version 4.03

2. Feasibility:

The number of dose-limiting toxicities that delay the time of planned surgery beyond the planned surgical window (>8 weeks) after completion of thoracic RT. DLTs will be collected and recorded according to CTCAE version 4.03

3. Surgical Morbidity and Mortality:

All adverse events (including serious and non-serious, as well as adverse events of special importance AESIs) or deaths that occur from the time of surgery until 30 days post-surgery or 100 days after the last dose of immunotherapy, whichever is longer.

Efficacy Assessments:

1. Pathologic Response Rate:

Pathologic response evaluated by two thoracic pathologists as described by Pataer et al (J Thorac Oncol 2012), and stratified into major pathologic response (MPR), partial response (PR) and no response (NR).

2. Radiologic Response:

Radiologic response by RECIST 1.1 and immune-related RECIST criteria.

3. Recurrence-Free Survival:

The time from study enrollment until radiologic evidence of local or distant recurrent NSCLC.

4. Overall Survival

The time from study enrollment until death from any cause.

Statistical methods:

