3.1.4. Treatment and Collection of Biological Specimens

Sixteen patients with resectable IIIA NSCLC (squamous and non-squamous) will receive preoperative durvalumab on days 1, 30 and 60, (week 1, 4, 8), concurrently with thoracic radiation weeks 1-5 (+/-2) before planned surgery on 6-8 weeks after completion of thoracic radiation. Thoracic radiation will be performed as part of standard of care, to a total of 45Gy in 25 fractions using standard radiation methods employed at the Sidney Kimmel Comprehensive Cancer Center at Johns Hopkins University. Serial peripheral blood samples for exploratory analyses will be collected prior to each dose of study drug(s), once within 3 days prior to surgery, and at a timepoint 30 days (+/- 7 days) after surgery, as detailed in Figure 1. Preoperative core biopsy of the primary tumor, and optional preoperative mediastinal lymph node biopsies, will be

18 Nov 2020 Page **56** of **164**

obtained. Archived or new tissue specimens will fulfill these criteria. Details of sample requirements are detailed in section 8.3. Specific procedures for accessioning specimens are outlined in detail in the laboratory manual. Patients will have one tumor imaging of the chest during the 7 days prior to surgery to re-assess tumor status and potential pulmonary inflammation following neoadjuvant treatment. Surgery for patients enrolled on this protocol will be according to generally accepted standards of care. It is advised that patients have at least 3 mediastinal and hilar lymph node stations sampled during surgery. The treatment plan is outlined in section 6.0

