12.3.2. Analysis Plan for Secondary Endpoints

Pathologic response will be stratified as showing MPR (>90% reduction in tumor cells), PR (10-90%) or NR (0-10%). The proportion of patient's whose tumor samples achieve MPR, PR and NR will be tabulated. The relationship between pathologic response in post-treatment resection specimens and clinical outcomes such as RFS, OS and surgical morbidity/mortality will be assessed through log-rank test and Cox proportional hazards (PH) model. Radiologic response will be evaluated by RECIST 1.1 and immunerelated RECIST criteria at time points specified in the Schedule of Assessments (Figure 1). The relationship between radiologic response in post immunoradiation CT scans and clinical outcomes including RFS, OS and surgical morbidity/mortality will be assessed using log-rank and Cox PH model. RFS will be defined as time from commencement of study therapy until the date of radiologic evidence of local or distant recurrent NSCLC. OS) will be defined as the time from commencement of protocol treatment until death due to any cause. RFS and OS will be calculated using the Kaplan-Meier method, and will be analyzed as time-to-event data. All adverse events that occur from the time of surgery until 30 days post-surgery or from the last dose of immunotherapy until 100 days, will be similarly summarized by type and grade. Any deaths that occur in this time period will be recorded. Attributions to the development of AEs or death in this time period will be recorded as either definitely related, possibly related, probably related or unrelated to study therapy.

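### Radiologic response, known only at the preoperative scan, is related to RFS and OS timed from first dose with no landmark, and the plan does not say how failures before or at that scan are handled

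*Combined protocol and SAP*

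**What the plan says.** Section 12.3.2 sets out to examine "The relationship between radiologic response in post immunoradiation CT scans and clinical outcomes including RFS, OS". Perioperative complications and deaths are listed as a further outcome. On method, the section says only that these associations "will be assessed using log-rank and Cox PH model". The time origins come in the same section: "RFS will be defined as time from commencement of study therapy until the date of radiologic evidence of local or distant recurrent NSCLC", while OS "will be defined as the time from commencement of protocol treatment until death due to any cause". The Protocol Synopsis uses a slightly different origin for RFS, "The time from study enrollment until radiologic evidence of local or distant recurrent NSCLC", but enrollment also precedes the scan, so the point is the same under either definition.

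The response scan comes much later. Section 3.1.4 says "Patients will have one tumor imaging of the chest during the 7 days prior to surgery to re-assess tumor status". Figure 1 places the pre-surgery visits at weeks 11-15, and its imaging footnote allows the scan up to 3 weeks before the planned operation. Figure 1 shows no tumor imaging between screening and that scan.

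Section 10.2.4 has RFS events detected on the scheduled CTs by RECIST 1.1 and censors deaths without recurrence. Section 10.2.3 derives each efficacy endpoint from RECIST 1.1.

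The documents give no landmark, no time-dependent covariate and no analysis set for this comparison. They give no rule for a patient without a preoperative scan, and they do not say whether progression on that scan is an RFS event.

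**The concern.** The groups being compared are formed from information that becomes available about 2.5-3.5 months after the clock starts. A patient who fails before or at the scan can never enter the responder group. Any such failure that is counted falls on the non-responders or drops out.

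The two outcomes are exposed in different ways. For RFS, early events can surface mainly at the response scan itself, since no earlier CT is scheduled. Progression there is non-response by definition. If it is also an RFS event, predictor and outcome are linked by construction, and leaving out unscanned patients does not help, because these patients were scanned. For OS, the problem arises only for deaths before the scan, and only if those patients are classed as non-responders.

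The plan commits to this correlation in Sections 10.2.2, 10.2.4 and 12.3.2. A spurious association could be read as support for radiologic response as a marker of later outcome.

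**Working it through.** The plan gives no sample size, alpha or effect size for this analysis, so it has no figure of its own to reproduce. A two-sided 5% level is assumed.

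**Inputs from the documents**
- Scan at weeks 11-15 (Figure 1), i.e. 11/4.345 = 2.53 to 15/4.345 = 3.45 months.
- Reference medians of 12.8 months for PFS (Section 10.2.4) and 23.6 months for OS (Section 10.2.5).
- Anticipated radiologic response of 60-65% (Section 10.2.2).
- 16 evaluable patients per cohort (Section 12.1), so 32 in all.
- Follow-up to 36 months (Section 10.2.5: years 1-3).

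**Share failing by the scan, constant hazard:** P = 1 - 2^(-t/median).
- RFS: 1 - 2^(-2.53/12.8) = 12.8%; 1 - 2^(-3.45/12.8) = 17.1%. This is 2.0 to 2.7 of 16.
- OS: 1 - 2^(-2.53/23.6) = 7.2%; 1 - 2^(-3.45/23.6) = 9.6%. This is 1.2 to 1.5 of 16.

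**Simulation with response independent of outcome (true HR 1).** Scan times are uniform over weeks 11-15, with 4,000-5,000 trials per setting.

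*RFS, every patient scanned, failures dated at the scan and counted as events, about 62% response among the rest.* Rejection by the nominal 5% log-rank test:

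| Failing by the scan | Clock from first dose | Landmark at scan |
|---|---|---|
| 2% (assumed) | about 7-8% | about 6-8% |
| 5% (assumed) | about 9-10% | about 6-8% |
| 10% (assumed) | 12-14% | about 6-8% |
| 12.8-month median, constant hazard | 17-22% | about 6-8% |

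The ranges cover 16 and 32 patients and repeated runs.

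*Failures before the scan, 60% response, reference medians:*

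| Outcome and rule | Rejection, n=16 | Rejection, n=32 | Apparent HR (60-65% response) |
|---|---|---|---|
| RFS, kept as non-responders | 14.0% | 19.3% | 0.65-0.67 |
| RFS, excluded, clock from first dose | 7.0% | 6.1% | 0.99-1.00 |
| RFS, landmark | 6.8% | 6.1% | 0.99-1.00 |
| OS, kept as non-responders | 9.9% | 10.7% | 0.71-0.74 |
| OS, excluded, clock from first dose | 6.2% | 5.0% | 1.00 |
| OS, landmark | 6.1% | 4.9% | 1.00 |

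Under the same keep-as-non-responder rule, 5% early failure (assumed) gives apparent HRs of 0.86-0.87 for RFS and 0.81-0.84 for OS. At 2% (assumed) they are 0.93-0.94 and 0.92-0.93.

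Taking both mechanisms together, the RFS rejection rate at the reference median spans 14-22%. The excess over 5% that remains with a landmark is small-sample error of the log-rank test.

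**Pathologic response.** Section 10.2.1 assesses it only in patients who reach resection. All groups therefore share the wait to surgery, and bias between them is small.

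**The case against.** The strongest reply is that the plan contains no rule making an unscanned patient a non-responder. The analysis concerns response on post-treatment CT scans, and a patient who fails earlier has no such scan. Section 2.2 also frames RFS and OS in patients whose immunoradiation is followed by surgery. If unscanned patients are left out, the comparison is unbiased even with the clock at first dose, as the calculation shows. This stands for OS. A reader might infer that early failures must be non-responders and that the planned analysis would favor responders whatever the truth. The documents do not support that reading. The analysis set is simply open: Section 4.4 follows all subjects for survival, while Section 3.1.2 replaces patients who leave during the DLT period.

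For RFS, the reply is that the event is *recurrent* disease, which need not include preoperative progression of an unresected tumor, and that Section 10.2.3 allows a confirmatory CT 4 weeks later. The definition is indeed open. But Section 10.2.4 ties event detection to scheduled CT by RECIST 1.1, so counting such progression is a natural reading, and excluding unscanned patients does not remove that link.

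It is also fair that a constant hazard at 12.8 months, a PFS figure from chemoradiation, probably overstates early failure in resectable, ECOG 0-1 patients expected to live over 6 months. An earlier scan, as the Figure 1 footnote permits, would lower it further. Finally, this is a secondary association with no alpha, power or decision attached.

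**Conclusion.** The concern holds in a conditional form. The stated method leaves failures before or at the response scan unhandled.
- **RFS:** predictor and outcome are linked by construction if preoperative progression by RECIST 1.1 counts as an event. False-positive rates are then about 9-10% with 5% failing by the scan and 12-14% with 10% (both assumed). The range of 14-22% at the reference median also covers early failures kept as non-responders, and is an upper range.
- **OS:** bias arises only if deaths before the scan are kept as non-responders. Rejection is then about 10-11% at the reference median, again probably an upper range. If those patients are excluded there is no bias.

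A landmark brings the error to about 6-8% in the RFS settings and removes the dependence on unstated rules. With 16 patients per cohort, the matter affects interpretation of one secondary association and does not touch the primary safety and feasibility conclusions. It is a low-severity, inexpensive improvement.

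**What to change.** In Section 12.3.2:
- Start the clock for the radiologic response-outcome analyses at the preoperative scan.
- Include only patients scanned, alive and event-free at that point. State that progression on the scan counts as an event, so those patients are excluded.
- Report the number excluded, by reason.
- For pathologic response, start the clock at surgery on the same principle.
- Keep first dose as time zero for the overall RFS and OS estimates.

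The cost is SAP wording. The downside is that about 1-3 of 16 patients per cohort leave this secondary association analysis, and its result then applies only to patients who reach the scan without failing.

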- 2. Feasibility: To evaluate whether durvalumab (cohort 1) or durvalumab plus tremelimumab (cohort 2) delivered concurrent with thoracic radiation (RT) and in the pre-surgical window prior to surgical resection, will not delay the time to surgery beyond the planned date of surgical resection, in patients with stage III resectable NSCLC.

Secondary Objective(s):

1. Pathologic Response

To determine whether durvalumab (cohort 1) or durvalumab plus tremelimumab (cohort 2) delivered concurrent with thoracic radiation (RT) and in the pre-surgical window prior to surgical resection, will induce a pathologic response in patient's primary tumors and draining lymph nodes, in patients with stage III resectable NSCLC.

2. Radiologic Response

To determine whether durvalumab (cohort 1) or durvalumab plus tremelimumab (cohort 2) delivered concurrent with thoracic radiation (RT) and in the pre-surgical window prior to surgical resection, will induce a radiologic response in in patient's primary tumors and draining lymph nodes, in patients with stage III resectable NSCLC.

3. Recurrence-Free Survival (RFS)

To determine whether durvalumab (cohort 1) or durvalumab plus tremelimumab (cohort 2) delivered concurrent with thoracic radiation (RT) and in the pre-surgical window prior to surgical resection, will delay the development of local or distant recurrent non-small cell lung cancer, in patients with stage III resectable NSCLC.

4. Surgical morbidity and mortality

To determine whether durvalumab (cohort 1) or durvalumab plus tremelimumab (cohort 2) delivered concurrent with thoracic radiation (RT) and in the pre-surgical window prior to surgical resection, will lead to unacceptable rates of postoperative morbidity or mortality when compared to historical controls, in patients with stage III resectable NSCLC.

5. Overall Survival

To determine whether durvalumab (cohort 1) or durvalumab plus tremelimumab (cohort 2) delivered concurrent with thoracic radiation (RT) and alone in the pre-surgical window prior to surgical resection, will result in an overall survival improvement in comparison to historical controls, in patients with stage III resectable NSCLC.

Exploratory Objective(s):

1. Genomic and neoantigen correlates.

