2.2. Secondary Objective(s)

- (1) Examine pathologic responses in post-treatment resection specimens, in patients with resectable stage III NSCLC treated with preoperative immunoradiation followed by surgery.
- (2) Examine radiologic responses in stage III resectable NSCLC treated with preoperative immunoradiation, using RECIST 1.1 and immune-related (ir) RECIST criteria
- (3) Evaluate recurrence-free survival (RFS) in patients with stage III resectable NSCLC treated with preoperative immunoradiation followed by surgery, where RFS is defined as the time from commencement of therapy until the development of local or distant recurrent disease.
- (4) Evaluate surgical morbidity and mortality in patients with stage III resectable NSCLC treated with preoperative immunoradiation followed by surgery, where morbidity is defined as the number treatment-related AEs, and mortality is the number of deaths, from the day of surgery until 30 days postoperatively or 100 days after the last dose of immunotherapy, whichever is longer.
- (5) Evaluate overall survival (OS) in patients with stage III resectable NSCLC treated with preoperative immunoradiation followed by surgery, where OS is defined as the time from commencement of therapy until death from any cause.

18 Nov 2020 Page **54** of **164**

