10.1.3. Surgical Morbidity and Mortality

[figure not shown]
Adverse events of any grade that occur in the postoperative period (day of surgery until 30 days post surgery), will be collected. These data will be obtained by weekly review of the subject's medical record by study investigators. The attributions of these AEs will also be recorded, as per section 9.3. Deaths that occur in the postoperative period will be recorded, and the attribution of any subject death will be recorded.

18-Nov-2020 Page **111** of **164**

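### Surgical morbidity and mortality is defined in four places that disagree, and the analysis section, read literally, admits events from before surgery

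*Combined protocol and SAP*

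**What the plan says.** The endpoint serves Secondary Objective 4 of the synopsis, which asks whether treatment leads to "unacceptable rates of postoperative morbidity or mortality when compared to historical controls". It is then defined four times:

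- **Synopsis, safety assessments, item 3:** all AEs, or "deaths that occur from the time of surgery until 30 days post-surgery or 100 days after the last dose of immunotherapy, whichever is longer".
- **Section 2.2, objective 4:** "morbidity is defined as the number treatment-related AEs, and mortality is the number of deaths, from the day of surgery until 30 days postoperatively", or until 100 days after the last dose if that is longer. The window matches the synopsis, but morbidity is limited to treatment-related events.
- **Section 10.1.3:** "Adverse events of any grade that occur in the postoperative period (day of surgery until 30 days post surgery), will be collected". There is no 100-day extension and no limit to related events; on attribution it says "The attributions of these AEs will also be recorded, as per section 9.3".
- **Section 12.3.2:** all AEs "from the time of surgery until 30 days post-surgery or from the last dose of immunotherapy until 100 days", summarised by type and grade, with deaths in that period recorded and attribution "recorded as either definitely related, possibly related, probably related or unrelated to study therapy". There is no longer-of rule.

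No section says which definition governs.

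**The concern.** In the synopsis and 2.2 the 100-day rule only sets the end of a window that starts at surgery. In 12.3.2 the same 100 days come with their own starting point, the last dose. Sections 5.2.1 and 5.2.2 place dose 3 in the pre-surgical window, so that starting point precedes the operation. A programmer working from 12.3.2 would put preoperative immune or radiation events into the only AE summary that section offers for a postoperative objective. The last-dose part of the window also does not require that surgery took place.

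The sections differ in two further ways. Section 10.1.3 stops at day 30, while the synopsis and 2.2 run well past it after full dosing. Section 2.2 alone drops events judged unrelated to treatment, which could remove ordinary surgical complications from the morbidity count.

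At stake is whether the postoperative rates can be compared with historical ones. Section 12.3.2 also relates pathologic response to surgical morbidity and mortality. That response is read from the resected specimen, so an event before surgery cannot be an outcome that follows it.

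**Working it through.** The plan gives no figure for this endpoint to reproduce, so the check is date arithmetic on the protocol's own schedule.

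**Inputs**
- Doses on days 1, 30 and 60, each ±3 days (Section 6.2.1).
- Surgery 6-8 weeks, i.e. 42-56 days, after RT ends (Section 6.2.1).
- RT end: days 25-28 (Section 6.2.1). Alternatively day 33, an assumption: 25 fractions at 5 per week (Section 6.2.2.3), Monday start, no breaks. The documents support both, so both are carried.
- Figure 1 puts the pre-surgical visits in weeks 11-15, taken here as surgery on days 71-105.

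**Formulas**
- Preoperative days in the last-dose part of 12.3.2 = surgery day − last-dose day.
- Synopsis and 2.2 window length = max(surgery day + 30, last-dose day + 100) − surgery day.
- 10.1.3 window length = 30 days.
- 12.3.2 window length, both parts combined = max(surgery day + 30, last-dose day + 100) − last-dose day.

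**Last dose on day 60** (60 + 100 = day 160)

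| Timing | Surgery day | Preoperative days in 12.3.2 | Synopsis and 2.2 window | 10.1.3 window | 12.3.2 window |
|---|---|---|---|---|---|
| RT ends day 33 | 33+42=75 to 33+56=89 | 75−60=15 to 89−60=29 | 160−89=71 to 160−75=85 | 30 | 100 |
| RT ends days 25-28 | 25+42=67 to 28+56=84 | 67−60=7 to 84−60=24 | 160−84=76 to 160−67=93 | 30 | 100 |
| Figure 1 weeks 11-15 | 71 to 105 | 71−60=11 to 105−60=45 | 160−105=55 to 160−71=89 | 30 | 100 |

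With surgery on days 75-89, the ±3-day dosing window gives 75−63=12 to 89−57=32 preoperative days.

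**Dosing stopped early, surgery on days 75-89.** Section 3.1.5 lets such patients proceed to surgery.
- Last dose on day 30: 75−30=45 to 89−30=59 preoperative days.
- Last dose on day 1: 75−1=74 to 89−1=88 preoperative days.

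**Start at surgery instead:** no preoperative days under any of these timings.

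**Illustration.** A death on postoperative day 45 after full dosing counts under the synopsis and 2.2, where the window is at least 55 days, but not under 10.1.3. If 16 patients were operated on, that is 1/16 = 6.25% or 0%. Section 3.1.6.2 cites a historical perioperative mortality in the order of 4%.

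**The case against.** Section 12.3.2 does not call these events surgical morbidity, and its sentence may be a loose paraphrase of the longer-of rule used in the synopsis and 2.2, both of which start at surgery. That is a fair reading of intent, and a flat statement that preoperative events will be counted as surgical goes further than the text. But the sentence as written moves the start of the window and not only its end, and it is the section's only AE summary for this objective.

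Section 10.1.3 can be read as a data-collection statement, since AEs are recorded for longer elsewhere (Section 9.3.1). That softens the conflict but does not say which window is analysed.

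A reader might infer that the same data could support opposite conclusions. The documents do not support that: they set no threshold or test for the comparison with historical controls, and attribution is recorded, so the related subset can be recovered. The treatment-related limit in 2.2 applies to morbidity only; deaths are counted without it. The 6.25% above assumes 16 operated patients and is not a decision boundary.

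A reader might also take 30 days as the historical window. Section 1.6.5 does not establish that. It reports 16 non-cancer deaths in one trial, 10 of them within 30 days of thoracotomy, and a 4% operative mortality in another series with no window stated.

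**Conclusion.** The concern holds as a conflict of definitions: four statements of one endpoint, with three different windows and two rules on which AEs count. Read literally, 12.3.2 admits 15-29 preoperative days if RT ends on day 33, and 7-45 days across the protocol's other timings with dose 3 on day 60. The span is longer if dosing stopped early, and patients never operated on could contribute events. These figures rest on the stated RT end dates, on reading the Figure 1 weeks as surgery dates, and on joining the two parts of the 12.3.2 window. The rate compared with historical controls depends on the section followed; the documents do not show how far, or in which direction, it would move. The endpoint is secondary and descriptive, and the primary endpoints and Bayesian stopping rules are unaffected. The wording should be corrected before the analysis.

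**What to change.** In 12.3.2, adopt the synopsis definition: among operated patients, all AEs and deaths from the day of surgery to the longer of 30 days after surgery and 100 days after the last dose. Tabulate by attribution and show the treatment-related subset. Name one attribution scale, because 12.3.2 has four levels, 9.2.2 has five and 9.3.2 is yes or no. Also tabulate the day 0-30 subset, which keeps the 10.1.3 window. Make any historical comparison on the window that the cited control rate uses, and state that window. Align 2.2 and 10.1.3 with the synopsis as well.

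The cost is wording and one extra tabulation. AE dates and causality are already collected under Section 9.3.
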